7.2.5 Duplicate 12-lead Electrocardiogram

Duplicate 12-lead ECGs will be performed after the participant has rested comfortably in the supine position for at least 3 minutes.

The following parameters will be assessed: heart rate, PR, RR, QRS, QT, QTcB (Bazett formula), QTcF (Fridericia formula). The Investigator (or a qualified delegate at the investigational site) will interpret the ECG using one of the following categories: within normal limits, abnormal but not clinically significant, or abnormal and clinically significant.

Clinically significant observations, as deemed by the Investigator, will be recorded as AEs.

7.2.6 Clinical Laboratory Assessments

Clinical laboratory samples will be analyzed by the site's local laboratory.

Blood samples will be collected for the following tests:

- Hematology: Hemoglobin, hematocrit, red blood cell count, white blood cell count (WBC), platelet count, differential WBC (neutrophils, eosinophils, basophils, lymphocytes, and monocytes), absolute neutrophil count, and absolute lymphocyte count.
- Biochemistry (pre-prandial): albumin, total protein, blood glucose, sodium, potassium, blood urea nitrogen, creatinine, calcium, uric acid, AST, ALT, total bilirubin, alkaline phosphatase.
- Coagulation: prothrombin time, activated partial thromboplastin time, D-dimer. *Note: Coagulation may be assessed at any other timepoint, outside of those specified in the Schedule of assessments, in case of an abnormal result, and followed until resolution.*
- eGFR: will be calculated from creatinine using the Chronic Kidney Disease Epidemiology Collaboration (CKD-EPI) formula and reported as mL/min. To convert mL/min/1.73 m2 to mL/min, multiply by the individual's Body Surface Area (calculated using the Mosteller formula) and divide by 1.73.
- Biochemical Markers: Serum testosterone.

Urine samples will be collected for the following tests:

• Urinalysis: to include determination of protein, glucose and leukocytes (dipstick test).

In the event of an unexplained, clinically significant abnormal laboratory test result, the test should be repeated and followed up until it has returned to the normal range and/or an adequate explanation of the abnormality is found.

During the study, all out of range (abnormal) laboratory values, except for PSA, must be evaluated and commented on by the Investigator (or a qualified delegated observer at the investigational site) for clinical significance using one of the following categories: within normal limits, abnormal but not clinically significant, or abnormal and clinically significant. Clinically significant observations will be recorded as AEs unless they are associated with a diagnosis that itself has been reported as an AE (e.g., raised white cells and fever associated with an infection – in this case the infection is the AE and the lab value and fever are signs and symptoms of the AE and should not be reported separately).

7.2.7 Total PSA

As part of Screening, baseline PSA will be assessed; additionally, PSA results and dates of 2 previous most recent measurements (prior measurements are needed to assess PSA velocity/doubling time), PSA at initial diagnosis and PSA after initial definitive treatment (nadir) must also be recorded on the eCRF.

Prostate-specific antigen will further be assessed during the Follow-Up as specified in the Schedule of assessments. However, if radiation therapy or other salvage focal therapy (e.g., cryotherapy) is initiated during the study (as long as no concomitant ADT is given), PSA levels must be monitored every 4 weeks from the initiation of the therapy. Prostate-specific antigen response (defined as total PSA decline by \geq 50% from baseline) must be confirmed by a second value within 4 weeks.

7.3 Imaging Assessments

7.3.1 Institutional Standard of Care Conventional Scan

Institutional SOC conventional scan (e.g., CT, MRI, whole-body ^{99m}Tc-MDP, ¹⁸F-fluciclovine, ¹¹C-choline, approved PSMA PET [such as ¹⁸F-DCFPyL or ⁶⁸Ga-PSMA-11]) must be performed within 60 days of Day 0.

For each imaging modality, the date of acquisition and result (as positive, negative or equivocal for recurrent PC) must be reported on the eCRF. If equivocal, the site(s) of equivocal disease is also to be reported.

All available scans completed within 60 days of Day 0 will be transferred in DICOM format to the central reading center with anonymization of participant specific information as specified in the Image Acquisition Manual.

7.3.2 ⁶⁴Cu-SAR-bisPSMA PET/CT

The site will conduct the quantitative PET/CT according to the Image Acquisition Manual, which contains details of scan acquisition, processing parameters and quality assurance procedures. For a given participant, the same scanner must be used for all scan acquisition timepoints.

Participants will be asked to void prior to imaging. After voiding, a whole-body low dose CT and PET scan will be acquired starting from the mid-thigh to the skull vertex. If no diagnostic quality anatomical imaging (CT or MRI) is available within 60 days of Day 0, a diagnostic quality CT must be acquired as part of the Day 0 PET/CT scan.

The PET/CT images will be transferred in DICOM format to the central reading center with anonymization of participant specific information as specified in the Image Acquisition Manual.

7.3.2.1 ⁶⁴Cu-SAR-bisPSMA PET/CT Local Interpretation

The ⁶⁴Cu-SAR-bisPSMA PET/CT scans will be interpreted locally by an appropriately qualified Investigator in a non-blinded fashion.

The reader will be required to evaluate the PET scans individually for the presence of pathological ⁶⁴Cu-SAR-bisPSMA uptake in the prostate bed/gland, pelvic lymph nodes, extra pelvic lymph nodes, visceral/soft tissue and bone. Computed tomography scans from the PET/CT will be available to the readers to guide anatomical localization.

A ⁶⁴Cu-SAR-bisPSMA PET-positive lesion will be defined as focal uptake that is greater than physiologic background uptake in that tissue or greater than adjacent background if no physiologic uptake is expected and judged by the reader to be suspicious for disease. The number of PET-positive lesion(s) in each anatomical subregion will be documented.

Any incidental findings on the ⁶⁴Cu-SAR-bisPSMA PET/CT scan(s) that are of potential clinical relevance and are not directly associated with the objectives of the protocol should be evaluated and handled by the investigator as per standard medical/clinical judgment.

The processes for image acquisition, transmittal, and interpretation, including the list of regions and subregions to be assessed on the ⁶⁴Cu-SAR-bisPSMA PET/CT are detailed in the Image Acquisition Manual.

7.3.2.2 ⁶⁴Cu-SAR-bisPSMA PET/CT Central Interpretation

The central reading center will receive and evaluate the ⁶⁴Cu-SAR-bisPSMA PET/CT scans. The scans will be interpreted by three different independent blinded readers in a random order at separate reading sessions. Central readers will be blinded as described in Section 4.3. Computed tomography scans from the ⁶⁴Cu-SAR-bisPSMA PET/CT will be available for anatomic correlation.

The readers will be required to evaluate the PET scans individually for the presence of pathological ⁶⁴Cu-SAR-bisPSMA uptake in the prostate bed/gland, pelvic lymph nodes, extra pelvic lymph nodes, visceral/soft tissue and bone. The same ⁶⁴Cu-SAR-bisPSMA PET-positive lesion definition will be applied as for the local interpretation. Lesions that do not meet the criteria for a positive lesion but are deemed suspicious for PC will be recorded as equivocal. The number of lesion(s) in each anatomical subregion will be documented. The size (two axial dimensions), location, standardized uptake value (SUV)mean and max, lesion-to-background ratio and reader confidence level will be recorded for up to 15 soft tissue lesions and 10 bone lesions by the central readers.

The processes for image acquisition, transmittal, and interpretation are detailed in the Image Acquisition Manual and Imaging Review Charter.

7.3.3 Follow-up Conventional Imaging

Follow-up conventional imaging must be acquired for all participants as specified in the Schedule of assessments, regardless of the ⁶⁴Cu-SAR-bisPSMA PET/CT findings.

The follow-up conventional imaging must include the same modality/modalities as the SOC conventional imaging performed at baseline to allow for reproducible and accurate comparisons and should include anatomical imaging (MRI or CT; a diagnostic quality CT completed as part of a PET/CT scan is acceptable) and molecular imaging (e.g., whole body ^{99m}Tc-MDP, ¹⁸F-fluciclovine, ¹¹C-choline, approved PSMA PET [such as ¹⁸F-DCFPyL or ⁶⁸Ga-PSMA-11]). Scan acquisition will be completed according to institutional protocols.

The imaging modality, date of acquisition and result (including number of lesions suspicious for PC within each anatomical subregion) must be recorded on the eCRF.

All scans will be transferred in DICOM format to the central reading center with anonymization of participant specific information as specified in the Image Acquisition Manual.

Note: Additional follow-up conventional imaging may be completed at any other timepoint, outside of those specified in the Schedule of assessments, as deemed appropriate by the Investigator. All follow-up scans acquired within 180 days (± 15 days) of Day 0 must be transferred to the central reading center.

7.4 Histopathology

Where clinically feasible, histopathology (from image-guided biopsy or surgery [e.g., salvage pelvic lymph node dissection]) should be obtained for as many ⁶⁴Cu-SAR-bisPSMA PET-positive lesions as possible based on the local interpretation of the ⁶⁴Cu-SAR-bisPSMA PET/CT scans. If clinically feasible, the Investigator should make every effort to obtain histopathology for at least one ⁶⁴Cu-SAR-bisPSMA PET-positive lesion **per region**. The biopsy or surgery specimens will be processed and analyzed locally. The local pathologist evaluating the samples will be blinded to the ⁶⁴Cu-SAR-bisPSMA PET/CT results.

The procedure, date of assessment, imaging modality used to guide biopsy (if applicable) and local histopathology result will be recorded on the eCRF.

For participants undergoing image-guided needle biopsy, the needle biopsy images (e.g., CT, transrectal ultrasound-MRI, ultrasound) of the procedure will be sent to central reading center. The instruction for capturing biopsy images and directions for submitting the images to the central reading center is specified in the Image Acquisition Manual.

All histopathology results (and any associated images) acquired within 180 days (± 15 days) of Day 0 must be transferred to the central reading center.

7.5 Diagnostic Efficacy Assessments

7.5.1 Assessment of the Composite Reference Standard

The composite Reference Standard may consist of histopathology, conventional imaging modalities that are routinely used in the diagnosis and staging of PC and PSA levels. ⁶⁴Cu-SAR-bisPSMA scans will not form part of the Reference Standard.

The Reference Standard status will be determined by an independent, blinded, central expert panel. The expert panel will establish the Reference Standard disease status (on a participant-and region-level) for each participant individually, using information provided by the site's Investigator. The experts will be blinded as described in Section 4.3.

The Investigator will be required to submit all relevant clinical evidence available for the participant to enable the assessment of the Reference Standard. Relevant evidence will include:

- All available histopathology reports related to the participants disease history;
- All available conventional scans and related local reports collected as part of Screening (within 60 days of Day 0) and Follow-up (within 180 days [±15 days] of Day 0);
- PSA levels recorded as part of Screening and Follow-up;
- All available PC related symptom and treatment history;

The composite Reference Standard will be hierarchical in nature, with three levels of evidence that will be applied as follows:

- Level 1: Evaluable histopathology from biopsy or surgery OR in case that histopathology is not available, inconclusive or negative:
- Level 2: Conventional imaging procedures OR if neither histopathology or conventional imaging are available or informative:
- Level 3: Confirmed PSA response following radiation or other salvage focal therapy (as long as no concomitant ADT is given), defined as total PSA decline by ≥50% from baseline, confirmed by a second value within four weeks as per the Prostate Cancer Working Group 3 criteria²⁵.

The expert panel will use the collective information to determine and record each region with histopathology demonstrating PC, the number of lesions suspicious for PC detected on conventional imaging in each anatomical subregion and whether the participant achieved confirmed PSA response (if applicable).

Region(s) with no histopathology demonstrating PC or no unequivocal lesion recorded in any of the anatomical subregions on conventional imaging will be deemed negative for the region level Reference Standard status.

Region(s) with histopathology demonstrating PC will qualify the region as positive for the region level Reference Standard status. A subregion with at least one unequivocal lesion (or

cluster of lesions or diffuse sclerotic metastasis) on conventional imaging will qualify the subregion as positive for the Reference Standard status.

If the expert panel judged that the available information is insufficient to provide a reliable conclusion, the result will be recorded as non-evaluable (e.g., no follow-up assessments were completed) or inconclusive. The reason for selecting a non-evaluable or inconclusive result will be documented.

Further details on the process and interpretation of the conventional imaging will be provided in the Imaging Review Charter.

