3.2 Study Duration, Beginning and End of Study

Participants are considered enrolled in the study once they are appropriately consented and screened, with eligibility verified by an Investigator.

The expected study recruitment period is ~6 months.

The maximum screening period for each participant is 28 days.

The maximum on study period for each participant is ~6 months.

The total trial duration is ~13 months.

The end of study is defined as the date of the final participant visit/contact.

In addition, the Sponsor may decide to terminate the study at any time (see Section 4.5).

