6.2 Permitted Treatments

All SOC treatments are permitted throughout the duration of the participant's involvement in the study with the exception of those treatments outlined in Section 6.3.

6.3 **Prohibited Treatments**

Treatment with investigational agents (that are likely to affect PSA levels or antineoplastic agents), saw palmetto, estrogens, steroids, testosterone supplements, 5ARIs (finasteride/dutasteride), and any antineoplastic therapy (with the exception of radiation or other salvage focal therapy with no concomitant ADT initiated following completion of Visit 4) is prohibited throughout the duration of the participant's involvement in the study.

Histopathological confirmation of PC prior to commencement of radiation or other salvage focal therapy is strongly encouraged.

Participants who receive prohibited treatment(s) should remain in the study until completion of Visit 4 to enable the assessment of safety.

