#### 7.0 STATISTICAL METHODS

#### 7.1 General Considerations

#### 7.1.1 Standard Calculations

- Variables requiring calculation will be derived using the following formulas:
- Baseline: A baseline value, unless specified otherwise, is the last non-missing value recorded prior to the Cu-SAR-bisPSMA administration. If an assessment has both a date and time that exactly match the date and time of first dose of study drug, the assessment will be counted as baseline. For participants who are enrolled, but not dosed, the last assessment collected on or prior to the enrollment date is considered baseline.
- Change from Baseline: Change from baseline will be calculated for each patient at the specified time point as the value at the specified time point minus the baseline value.
- Study Day: The day of Cu-SAR-bisPSMA administration will be on Day 0 as specified in the study protocol schedule of events, but for Clinical Data Interchange Standards Consortium (CDISC) compliance, the study day variables will consider this as "Day 1" as there cannot be a Day 0. Study listings will be presented as "Day 0" to match the protocol.
- For a given date, study day is calculated in the SDTM data as days since the date of single dose of Cu-SAR-bisPSMA:
  - Study day = date dose date + 1, where date  $\geq$  dose date
  - Study day = date dose date, where date < dose date
- For a given date, study day is calculated in the TLF presentations as days since the date of single dose of Cu-SAR-bisPSMA:
  - Study day = date dose date, where date  $\geq$  dose date
  - Study day = date dose date, where date < dose date
- Days: Durations, expressed in days, between one date (date1) and another later date (date2) are calculated according to the following formula: duration in days = (date2 date1 + 1).

September 4, 2024 CONFIDENTIAL Page 16 of 46

■ Body Mass Index (BMI): BMI  $(kg/m^2)$  = weight  $(kg) / [[height (cm)/100]^2]$ .

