## 7.6 Calculation of PSA Doubling Time and PSA Velocity

The following values of PSA are collecting for this study:

- PSA at Initial Diagnosis
- Nadir PSA after initial definitive treatment
- Most Recent PSA prior to screening #1 and #2
- Screening PSA
- PSA taken during the study at day 90 and 180 (if appliable) or after start of salvage focal therapy (can vary)

PSA doubling time (PSADT) and PSA velocity will be calculated at baseline and during the study and require different definitions. PSA at initial diagnosis will not be used for any calculations of PSA velocity or PSADT.

For calculation of PSADT and PSA velocity at **Baseline**, which will be calculated for all participants:

- PSA Velocity = Slope of the line of best fit using all available data within 12 months prior to screening as well as screening value (excluding at initial diagnosis).
- PSADT = ln(2) / ((ln(PSA value at screening) ln(oldest PSA value within 12 months prior to screening)) / (# of months from oldest PSA value within 12 months prior to PSA at screening))

September 4, 2024 CONFIDENTIAL Page 18 of 46

For calculation of PSADT and PSA velocity for on-study measurements, only the last measure of PSA taken during the study will be used. The following calculations will be done for PSA measurements **Post-Baseline**:

- PSA Velocity = Slope of the line of best fit using all available data on-study, including screening value.
  - o If the participant initiated radiation therapy on-study, the last PSA value is instead the last PSA value PRIOR to initiating radiation therapy.
- PSADT = ln(2) / ((ln(Last on-study PSA value) ln(PSA at screening)) / (# of months from last on-study PSA value to PSA at screening))
  - o If the participant initiated radiation therapy on-study, the last PSA value is instead the last PSA value PRIOR to initiating radiation therapy.
- If a participant has no post-screening value prior to initiation of radiation therapy, they will be excluded from post-baseline calculations of PSADT and PSA velocity.

For the calculation of the line of best fit for PSA Velocity, the following equations will be used for each participant, where  $x_i$  is the date of the measurement in months from screening (screening is x = 0) for each value,  $y_i$  is the PSA value, and n is the total number of datapoints for the participant for that calculation:

$$\overline{X} = \frac{\sum_{i=1}^{n} x_i}{n} \quad \overline{Y} = \frac{\sum_{i=1}^{n} y_i}{n}$$

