## • Non-evaluable:

o A region that has either non-evaluable (NE) Cu-SAR-bisPSMA PET/CT results for a specific timepoint (Day 0 or Day 1) or has a non-evaluable or inconclusive Reference Standard will not be assigned for that timepoint.

Assessments of **Participant-Level** Reference Standard against the Cu-SAR-bisPSMA PET/CT results:

• True Positive:

September 4, 2024 CONFIDENTIAL Page 22 of 46

- A participant with at least one TP region and/or at least one unequivocal Cu-SAR-bisPSMA positive lesion in any region and a confirmed PSA response to radiation or other salvage focal therapy.
  - Confirmed PSA response following radiation or other salvage focal therapy (as long as no concomitant ADT is given) = total PSA decline ≥50% from baseline, confirmed by a 2nd value within 4 weeks per Prostate Cancer Working Group 3 criteria.

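### PSA response to focal therapy is measured from the Screening PSA, so where PSA rises before therapy a fall of 50% or more can go unrecorded and lower participant-level CDR

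*Protocol*

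**What the plan says.** Protocol 7.5.1 ranks the reference evidence as histopathology, then conventional imaging, then a confirmed PSA response to radiation or other salvage focal therapy without ADT. That response is "defined as total PSA decline by ≥50% from baseline, confirmed by a second value within four weeks". SAP 7.8 repeats the rule as "total PSA decline ≥50% from baseline".

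Neither section says which PSA is the baseline. Two other places do:

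- Protocol 7.2.7: "As part of Screening, baseline PSA will be assessed". The same section goes on to define PSA response from baseline.
- SAP 7.1.1: unless specified otherwise, a baseline value "is the last non-missing value recorded prior to the" tracer administration. Nothing in the SAP specifies otherwise for PSA response.

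On timing, Protocol 6.3 exempts from the treatment ban only "radiation or other salvage focal therapy with no concomitant ADT initiated following completion of Visit 4", and Visit 4 is Day 7 ± 2. Protocol 3.2 adds: "The maximum screening period for each participant is 28 days". Scheduled PSA is at Screening, Day 90 and, where Visit 6 applies, Day 180. Once focal therapy begins, PSA is also taken every 4 weeks from its start.

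Under Protocol 7.5.2 and SAP 7.8, a PET-positive participant is true positive with either a true-positive region or a confirmed PSA response. Otherwise he is false positive; the SAP adds that the Reference Standard must be evaluable.

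**The concern.** The criterion is meant to show that treating the focal disease brought PSA down. Its reference value always predates the therapy, by at least the interval from Screening to Visit 4 and possibly by months. Entry requires suspected recurrence on PSA grounds, so any drift between the two is expected to be mostly upward. A man whose PSA has risen must then lose the interim rise as well as half of the Screening value. The same label therefore demands a larger response from men with fast PSA kinetics or late therapy.

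A missed response matters because it can be the only route to true-positive status for a PET-positive man whose follow-up imaging stays negative. He remains in the denominator of participant-level CDR, a co-primary endpoint, without counting in its numerator. The required fall also varies with PSA doubling time, which SAP 9.14.3.2 uses as a subgroup variable for CDR and PPV.

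**Working it through.** **The plan's own figure.** Inputs from Protocol 10.3: 40 evaluable, assumed CDR 42%, lower limit of the two-sided 95% exact interval above 20%. The smallest qualifying count is 14/40 (Clopper-Pearson lower limit 20.6%; 13/40 gives 18.6%). P(X ≥ 14 | n = 40, p = 0.42) = 85.5%, which agrees with the stated power of more than 85%. Enrolment is 40 / (1 − 0.20) = 50. The sample size is not at issue.

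**Fall needed from the pre-therapy PSA.** Assume PSA grows exponentially from Screening to the start of therapy, with a gap of g days and doubling time D months:

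- growth factor f = 2^(g / (30.44 × D))
- required fall from the pre-therapy PSA = 1 − 0.5 / f

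The doubling times are chosen to span the SAP 9.14.3.2 categories (<3.0 to ≥15.0 months). The 118-day gap takes Screening 28 days before Day 0 and therapy at Day 90 (28 + 90). The 60-day gap is an assumed shorter case.

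| Doubling time (months) | Gap 60 days: f, fall needed | Gap 118 days: f, fall needed |
|---|---|---|
| 3 | 1.58, 68% | 2.45, 80% |
| 6 | 1.26, 60% | 1.56, 68% |
| 9 | 1.16, 57% | 1.35, 63% |
| 15 | 1.10, 54% | 1.20, 58% |

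With the pre-therapy PSA as reference, every cell would read 50%.

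**One case (assumed values).** Screening PSA 1.0, doubling time 3 months, therapy three months later at PSA 2.0, confirmed fall to 0.9. From the pre-therapy value the fall is 1 − 0.9/2.0 = 55%; from Screening it is 1 − 0.9/1.0 = 10%. No response is recorded.

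**Effect on CDR.** One lost true positive is 1/40 = 2.5 points. The documents do not give the number lost, so this is a range:

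| Responders lost | Expected CDR | Power (14 or more of 40) |
|---|---|---|
| 0 | 42.0% | 85.5% |
| 1 | 39.5% | 77.0% |
| 2 | 37.0% | 66.0% |
| 3 | 34.5% | 53.3% |

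In observed counts, 17/40 is 42.5% (95% CI 27.0% to 59.1%). Losing three gives 14/40 = 35.0% (lower limit 20.6%). Losing four gives 13/40 = 32.5% (lower limit 18.6%, below 20%).

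**Planned sensitivity analyses.** The worst-case and tipping-point analyses in SAP 9.14.1.1 vary missing, non-evaluable or (worst case only) inconclusive reference data. Neither reopens an evaluable classification reached with the Screening anchor.

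**The case against.** The strongest reply is that few participants can be affected. A man must be PET-positive, receive focal therapy without ADT, have no true-positive region, have an evaluable Reference Standard, and have a fall that meets 50% from the pre-therapy PSA but not from Screening. Day 90 imaging is required of everyone, and one matching positive subregion already makes him true positive. This stands.

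A reader might infer that missed responders in general become false positives in the co-primary endpoints. The documents do not support that:

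- If the panel finds the evidence insufficient, the result is non-evaluable or inconclusive and the participant is left unassigned. False positive arises mainly when follow-up imaging is evaluable and negative.
- CDR has no false-positive term; the loss there is a non-true-positive in the denominator.
- Region-level PPV, the other co-primary measure, does not use PSA response, which is matched at participant level only.

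Nor is SAP 7.6 a precedent for another baseline. Its rule that "the last PSA value is instead the last PSA value PRIOR to initiating radiation therapy" keeps treated values out of the kinetics; Screening remains the starting point, and only radiation is named.

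Other points also stand. At long doubling times the required fall stays near 50%. Inclusion criterion 5a accepts a detectable PSA as well as a rising one, and Protocol 6 advises against enrolling men known to need ADT for rapidly rising PSA before findings can be verified. The Screening anchor is uniform and errs on the conservative side, and SAP 4.1 plans no formal hypothesis test. The Reference Standard Review Panel Charter and the programming supplement, not seen here, may fix the anchor. That possibility does not cure the rule as written in the protocol and SAP.

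**Conclusion.** The point holds within limits. As written, PSA response is judged against a value taken before the tracer dose, and so always before the therapy. Where PSA rises in between, a fall of 50% or more from the pre-therapy level can go unrecorded. Under exponential growth the fall needed is about 54% to 68% at 60 days and 58% to 80% at 118 days, for doubling times of 15 down to 3 months.

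The result is a downward bias in participant-level CDR of 2.5 points per case at 40 evaluable, with matching false positives in participant-level PPV and FPR. It cannot inflate a claim. A reader might take the loss of power to 53.3% as a forecast; it assumes three affected participants, and nothing in the documents supports that or any other count. The conclusion rests on reading baseline through Protocol 7.2.7 and SAP 7.1.1, and on the assumed growth model for the size.

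**What to change.** This changes an analysis definition only; it requires no change in treatment or visits.

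1. In SAP 7.8 and Protocol 7.5.1, define the reference PSA for response as the last PSA on or before the first day of focal therapy. Use the Screening PSA only when no later pre-therapy value exists.
2. List the anchor value, its date and the therapy start date for each participant assessed at Level 3.
3. Report CDR and participant-level PPV under both anchors, as a sensitivity analysis alongside those in SAP 9.14.1.1.

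The cost is a few lines in each document, the same definition in the panel charter and programming supplement, one listing and one extra table. The data are those already collected.

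The limit is real. For therapy started before Day 90 there is often no scheduled PSA after Screening, so unless an unscheduled or initiation-day value exists the fallback applies and the classification does not change. The change helps chiefly for therapy starting at or after the Day 90 visit. Anchors will then differ between participants and some bias will remain, which is why the listing and the two-anchor report are needed.
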